#### Testing strategy to control type I error:

Event rates will be compared between groups using the following hierarchical testing strategy:

- a. Non-inferiority of EVR+rCNI vs. MPA+sCNI will be evaluated based on the primary endpoint of tBPAR or eGFR (MDRD4)  $< 50 \text{ mL/min/1.73m}^2$  at Month 12 using a 10% non-inferiority margin (see [Section 2.5.2.1](#)).
- b. Non-inferiority of EVR+rCNI vs. MPA+sCNI will be evaluated with a 10% non-inferiority margin for the key secondary endpoint of tBPAR, graft loss or death at Month 12 (see [Section 2.6.2](#)).
- c. Superiority of EVR+rCNI to MPA+sCNI will be evaluated based on the primary endpoint of tBPAR or eGFR (MDRD4)  $< 50 \text{ mL/min/1.73m}^2$  at Month 12 (see [Section 2.5.2.2](#)).

The above hierarchical fixed hypothesis testing procedure will not inflate overall Type I error rate. Therefore, each hypothesis will be tested at the one-sided 0.025 significance level and no multiplicity adjustment is needed. For these statistical tests, one-sided p-values will be presented in the analysis outputs.

### 2.5.2.1 Non-Inferiority of Everolimus Plus Reduced CNI to MPA Plus Standard CNI

#### The null hypothesis:

$H_{01}$ :  $R_{\text{EVR+rCNI}} - R_{\text{MPA+sCNI}} \geq 0.10$  (non-inferiority margin): the difference in proportion of patients experiencing tBPAR or eGFR (MDRD4)  $< 50 \text{ mL/min/1.73m}^2$  at 12 months between the everolimus plus reduced CNI ( $R_{\text{EVR+rCNI}}$ ) and the MPA plus standard CNI arm ( $R_{\text{MPA+sCNI}}$ ) is at least 10%.

#### The alternative hypothesis:

$H_{A1}$ :  $R_{\text{EVR+rCNI}} - R_{\text{MPA+sCNI}} < 0.10$  (non-inferiority margin): The difference in proportion of patients experiencing tBPAR or eGFR (MDRD4)  $< 50 \text{ mL/min/1.73m}^2$  at 12 months between the everolimus plus reduced CNI ( $R_{\text{EVR+rCNI}}$ ) and the MPA plus standard CNI arm ( $R_{\text{MPA+sCNI}}$ ) is less than 10%.

The proportion of patients meeting the primary endpoint of tBPAR or eGFR (MDRD4)  $< 50 \text{ mL/min/1.73m}^2$  at Month 12 will be compared using a confidence interval approach.

Multiple imputation will be used as the primary method for handling missing data (see [Section 2.5.3](#) and [Section 4.2.1.1](#) for detail). The analysis first creates multiple (100) imputations of missing eGFR (MDRD4) values under a missing at random (MAR) assumption, resulting in multiple (100) imputed datasets. The imputation model assumes a multivariate normal model for the eGFR (MDRD4) measurements. This model will be estimated separately within each treatment stratum. Together with the tBPAR data, the binary composite endpoint of tBPAR or eGFR (MDRD4)  $< 50 \text{ mL/min/1.73m}^2$  at Month 12 post-transplantation will be derived.

To the resulting 100 imputed datasets, the proportion of patients meeting the primary endpoint of tBPAR or eGFR (MDRD4)  $< 50 \text{ mL/min/1.73m}^2$  at Month 12 will be estimated, yielding 100 sets of parameter estimates and associated covariance matrices. The analysis results are then combined according to Rubin's rules to derive overall estimates and confidence intervals that adequately reflect missing data uncertainty as well as associated p-values (see [Section 4.7.1](#) for sample analysis codes). The everolimus plus reduced CNI arm will be claimed to have a

non-inferior incidence of tBPAR or eGFR (MDRD4)  $< 50$  mL/min/1.73m^2 compared to the MPA plus standard CNI arm if the upper limit of the 95% CI is below 10%.

### 2.5.2.2 Superiority of Everolimus Plus Reduced CNI to MPA Plus Standard CNI

#### The null hypothesis:

H03:  $R_{\text{EVR+tCNI}} - R_{\text{MPA+sCNI}} \geq 0$ : the proportion of patients experiencing tBPAR or eGFR (MDRD4)  $< 50$  mL/min/1.73m^2 at 12 months in the everolimus plus reduced CNI (REVR+tCNI) arm is greater than or equal to that in the MPA plus standard CNI arm (RMPA+sCNI) arm.

#### The alternative hypothesis:

HA3:  $R_{\text{EVR+tCNI}} - R_{\text{MPA+sCNI}} < 0$ : the proportion of patients experiencing tBPAR or eGFR (MDRD4)  $< 50$  mL/min/1.73m^2 at 12 months in the everolimus plus reduced CNI (REVR+tCNI) arm is less than that in the MPA plus standard CNI arm (RMPA+sCNI) arm.

Following the aforementioned hierarchical fixed hypothesis testing procedure, the hypothesis H03 for superiority of EVR plus reduced CNI to MPA plus standard CNI will be evaluated only if non-inferiority of EVR plus reduced CNI vs. MPA plus standard CNI is achieved for the primary endpoint (rejecting the hypothesis H01) and the key secondary endpoint of tBPAR, graft loss or death at Month 12 (rejecting the hypothesis H02, see [Section 2.6.2](#)). The everolimus plus reduced CNI arm will be claimed to be superior to the MPA plus standard CNI arm with respect to composite endpoint of tBPAR or eGFR (MDRD4)  $< 50$  mL/min/1.73m^2 at 12 months if the upper limit of the 95% CI estimated in [Section 2.5.2.1](#) is less than 0.

### 2.5.3 Handling of Missing Values/Censoring/Discontinuations

Since the patients who have prematurely discontinued study regimen are followed on standard of care, renal function data (e.g. creatinine) and kidney allograft biopsy data will be collected post discontinuation of study regimen for these visits, it is expected that few patients would be missing efficacy and/or renal function evaluation for the 12 month analysis.

For the component of eGFR  $< 50$  mL/min/1.73m^2, a value for missing eGFR as a continuous variable will be imputed first (see [Section 4.2.1.1](#) for the main imputation), then dichotomized it to derive this endpoint. As allograft biopsy data will be collected on an as needed basis due to the nature of kidney transplant studies, no particular rule for missing biopsy will be applied.

### 2.5.4 Supportive Analyses

#### 2.5.4.1 Analysis on Treatment Compliant Patients

The analysis outlined for the primary endpoint in [Section 2.5.2](#) will be repeated using Compliant Set.

#### 2.5.4.2 Analysis on Per-Protocol Set

The analysis outlined for the primary endpoint in [Section 2.5.2](#) will be repeated using the Per-Protocol Set.

### 2.5.4.3 Subgroup Analysis

Subgroup analyses will be done for the primary composite endpoint of tBPAR or eGFR (MDRD4) < 50 mL/min/1.73m^2 at 12 months for the subgroups defined in [Section 2.2.1](#). Subgroup analyses will use similar methods described in [Section 2.5.2.1](#).

### 2.5.4.4 Analyses with Other Imputations for Missing eGFR (MDRD4) at Month 12

In addition to the main imputation, additional imputation method assuming missing not at random (MNAR) as provided in [Section 4.2.1.2](#) will be used to impute missing 12-month eGFR value to define the primary variable – composite endpoint of tBPAR or eGFR (MDRD4) < 50 mL/min/1.73m^2. With these imputations, non-inferiority and superiority analyses described in [Section 2.5.2](#) will be repeated.

## 2.6 Analysis of Key Secondary Objective

### 2.6.1 Key Secondary Endpoints

The key secondary endpoint is the binary composite efficacy failure of tBPAR, graft loss or death at Month 12 post-transplantation.

### 2.6.2 Statistical Model, Hypothesis, and Method of Analysis

For the key secondary objective regarding the composite efficacy failure of tBPAR, graft loss or death, the following hypotheses will be evaluated ( $\alpha=0.025$ , one-sided) only if non-inferiority of EVR plus reduced CNI vs. MPA plus standard CNI is achieved for the primary endpoint (rejecting the hypothesis  $H_{01}$ ), and will be based on the Full Analysis Set:

**The null hypothesis:**

$H_{02}$ :  $REVR_{+CNI} - R_{MPA+sCNI} \geq 0.10$  (non-inferiority margin): the difference in Kaplan-Meier event rate of the composite efficacy failure of tBPAR, graft loss or death at 12 months between the everolimus plus reduced CNI ( $REVR_{+CNI}$ ) and the MPA plus standard CNI arm ( $R_{MPA+sCNI}$ ) is at least 10%.

**The alternative hypothesis:**

$H_{A2}$ :  $REVR_{+CNI} - R_{MPA+sCNI} < 0.10$  (non-inferiority margin): the difference in Kaplan-Meier event rate of the composite efficacy failure of tBPAR, graft loss or death at 12 months between the everolimus plus reduced CNI ( $REVR_{+CNI}$ ) and the MPA plus standard CNI arm ( $R_{MPA+sCNI}$ ) is less than 10%.

For this analysis, the event rate of the composite efficacy failure of tBPAR, graft loss or death will be estimated with Kaplan-Meier product-limit formula. Greenwood's formula will be used to estimate variance of failure rates and to derive Z-test based confidence interval for the difference in failure rate between the everolimus plus reduced CNI and the MPA plus standard CNI arm.

A Kaplan-Meier table and plot will be produced. The differences between the two KM curves, corresponding to the two treatment arms, will be tested pair-wise using the log-rank test. In

these analyses, patients with event-free will be censored with the censoring time as defined as the Last Contact Day.

### **2.6.3 Handling of Missing Values/Censoring/Discontinuations**

Since the patients who have prematurely discontinued study regimen are followed on standard of care, efficacy data including kidney allograft biopsies will be collected post-discontinuation of study regimen for these visits, it is expected that few patients would be missing efficacy evaluation for the 12 months analysis. Patients with missing efficacy evaluation for the 12 month analysis will be censored at the latest day known to be free of the event.

### **2.6.4 Supportive Analyses**

As supportive analyses, this non-inferiority analysis will be repeated using the Per-Protocol Set. Based on FAS, Kaplan-Meier event rates at Month 12 will be summarized for the subgroups defined in [Section 2.2.1](#).

## **2.7 Analysis of Other Secondary Objective**

### **2.7.1 Other Secondary Endpoints**

Other secondary efficacy variables to be considered are as follows:

1. Composite endpoint of tBPAR or eGFR (MDRD4)  $< 50$  mL/min/1.73m^2 at Month 24
2. Composite endpoint of tBPAR excluding grade IA rejections or eGFR (MDRD4)  $< 50$  mL/min/1.73m^2 at Months 12 and 24
3. Composite efficacy failure of tBPAR, graft loss, or death at Month 24
4. Composite efficacy failure of tBPAR, graft loss, death, or loss to follow-up at Month 12 and 24
5. Components of composite efficacy failure as well as BPAR, AR, tAR at Month 12 and Month 24
  - a. AR
  - b. tAR
  - c. BPAR
  - d. tBPAR
  - e. tBPAR excluding grade IA rejections;
  - f. Humoral rejection
  - g. Graft loss
  - h. Death.
6. Composite endpoint of tBPAR, graft loss, death or eGFR  $< 50$  mL/min/1.73m^2 at Months 12 and 24
7. Composite endpoint of graft loss or death at Month 12 and Month 24
8. Composite endpoint of BPAR, graft loss or death at Month 12 and Month 24
9. eGFR (MDRD4)  $< 50$  mL/min/1.73m^2 at Month 12 and Month 24

10. Renal function (eGFR by MDRD4, CKD-EPI and Cystatin C-based formulae) at Month 12 and Month 24
11. Renal function change from Week 4 to Month 12 and Month 24
12. Evolution of renal function (eGFR by MDRD4) from Week 4 to Month 12 and Month 24 (slope analyses).

## 2.7.2 Statistical Model, Hypothesis, and Method of Analysis

### 2.7.2.1 Endpoints with eGFR (MDRD4) < 50 mL/min/1.73m^2 as a Component

Similar analysis method used for primary endpoint ([Section 2.5.2.1](#)) will be performed for the endpoint of eGFR (MDRD4) < 50 mL/min/1.73m^2 and the composite endpoints with eGFR (MDRD4) < 50 mL/min/1.73m^2 as a component based on the FAS. Difference between the event rates, and the corresponding 95% confidence interval and p-value for equality test will be provided. The multiple imputation presented in [Section 4.2.1.1](#) will be applied for missing eGFR (MDRD4) values.

- eGFR (MDRD4) < 50 mL/min/1.73m^2 at Months 12 and 24
- composite endpoint of tBPAR or eGFR (MDRD4) < 50 mL/min/1.73m^2 at Month 24
- composite endpoint of tBPAR excluding grade IA rejections or eGFR (MDRD4) < 50 mL/min/1.73m^2 at Months 12 and 24
- composite endpoint of tBPAR, graft loss, death or eGFR (MDRD4) < 50 mL/min/1.73m^2 at Months 12 and 24

In addition, the composite endpoint of tBPAR or eGFR (MDRD4) < 50 mL/min/1.73m^2 at Month 24 will be analyzed in similar manner based on compliant set population. The endpoint of eGFR (MDRD4) < 50 mL/min/1.73m^2 at Month 12 will be summarized on the FAS for the subgroups defined in [Section 2.2.1](#).

### 2.7.2.2 Endpoints without eGFR (MDRD4) < 50 mL/min/1.73m^2 as a Component

Based on FAS, for the composite efficacy failure (tBPAR, graft loss or death) at Month 24 and the composite endpoint of BPAR, graft loss or death at Month 12 and Month 24, Kaplan-Meier event rates will be estimated and compared between the everolimus plus reduced CNI and the MPA plus standard CNI arm. Similarly Kaplan-Meier event rates will be estimated and compared for AR, tAR, BPAR, tBPAR, tBPAR excluding grade IA rejections, AMR, graft loss, death, the composite endpoint of graft loss or death, and composite endpoint of tBPAR, graft loss, death, or loss to follow-up at Months 12 and 24. Kaplan-Meier event rate difference, 95% confidence interval and p-value for equality test will be provided. To assess time-to-event occurrence, Kaplan-Meier tables and plots will be produced with a log-rank test p-value for the above variables.

In addition, severity of tBPAR will be tabulated by treatment. The endpoint of tBPAR at Month 12 will be summarized on the FAS for the subgroups defined in [Section 2.2.1](#)

Forest plots of event rate differences for **all** efficacy endpoints specified in [Section 2.7.2](#) will be produced on the FAS.

## 2.7.3 Analysis of Renal Function Endpoints

Formulas for computing GFR endpoints can be found in [Section 4.5](#).

### 2.7.3.1 eGFR by CKD-EPI and Cystatin C-based Formulae

The renal function (eGFR by CKD-EPI and Cystatin C-based formulae) analyses will be based on on-treatment analysis without imputation. Renal function and change from Week 4 will be summarized by visit with descriptive statistics. A two-sided t-test will be performed to compare the two treatment groups at each visit. A plot of mean and 95% CI of eGFR by visit will be provided.

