2.2 Secondary objectives

Key Secondary Objectives

- To evaluate everolimus with reduced exposure CNI compared to MPA plus standard exposure CNI at 12 months post-transplantation with respect to the composite efficacy failure rate of (treated biopsy proven acute rejection (tBPAR), graft loss or death).
- To evaluate the binary composite endpoint of tBPAR or eGFR < 50 mL/min/1.73m² (MDRD4) Month 12 among compliant subjects.

Other Secondary Objectives

To evaluate, by treatment group;

- The incidence of composite endpoint of tBPAR or eGFR < 50 mL/min/1.73m² (MDRD4) at Month 24.
- The incidence of composite endpoint of tBPAR (excluding Banff grade 1A acute rejections) or eGFR < 50 mL/min/1.73m² (MDRD4) at Month 24.
- The incidence of composite endpoint of tBPAR or eGFR < 50 mL/min/1.73m² (MDRD4) at Month 12 by subgroup (see Section 9.4.4).

- The incidence of composite endpoint of tBPAR, graft loss or death at Month 24.
- The incidence of composite endpoint of tBPAR, graft loss, death, or loss to follow-up at Months 12 and 24.
- The incidence of composite endpoint of tBPAR, graft loss, death or eGFR < 50 mL/min/1.73m² at Months 12 and 24.
- The incidence of composite endpoint of graft loss or death at Month 12 and 24.
- The incidence of individual endpoints of death, graft loss, tBPAR, BPAR, tAR, AR and humoral rejection at Months 12 and 24.
- The incidence of tBPAR by severity and time to event.
- The incidence of tBPAR excluding Banff 1A grade acute rejections
- The incidence of transplant recipients with eGFR < 50 mL/min/1.73m² at Months 12 and 24.
- Renal allograft function and change in renal allograft function from Month 1 (eGFR) at Months 12 and 24.
- The evolution of renal function, as eGFR, over time by slope analysis.
- Renal function by Cystatin C-based and other alternate formulae (e.g. CKD-EPI).
- The incidence of adverse events, serious adverse events and adverse events leading to study regimen discontinuation.
- The incidence of CMV and BKV, new onset diabetes mellitus, chronic kidney disease with associated proteinuria and CNI associated adverse events.
- Urinary protein and albumin excretion by treatment estimated by urinary protein/creatinine and urinary albumin/creatinine ratios.
- The incidence of major cardiovascular events.
- The incidence of malignancies.

3 Investigational plan

[figure not shown]

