9.5.2 Other secondary efficacy variables

Other secondary efficacy variables to be considered are as follows:

- (1) Composite endpoint of tBPAR or eGFR (MDRD4) < 50 mL/min/1.73m² at Month 24;
- (2) Composite endpoint of tBPAR excluding grade IA rejections or eGFR (MDRD4) < 50 mL/min/1.73m² at Months 12 and 24
- (3) Composite efficacy failure of tBPAR, graft loss, or death at Month 24;
- (4) Composite efficacy failure of tBPAR, graft loss, death, or loss to follow-up at Month 12 and 24;
- (5) Components of composite efficacy failure as well as BPAR, AR, tAR at Month 12 and Month 24;
 - a) AR
 - b) tAR
 - c) BPAR;
 - d) tBPAR;
 - e) tBPAR excluding grade IA rejections;
 - f) Humoral rejection
 - g) Graft loss;
 - h) Death.
- (6) composite endpoint of tBPAR, graft loss, death or eGFR < 50 mL/min/1.73m² at Months 12 and 24;
- (7) Composite endpoint of graft loss or death at Month 12 and Month 24;
- (8) Composite endpoint of BPAR, graft loss or death at Month 12 and Month 24;
- (9) eGFR (MDRD4) $< 50 \text{ mL/min}/1.73\text{m}^2$ at Month 12 and Month 24;
- (10) Renal function (eGFR by MDRD4, CKD-EPI and Cystatin C-based formulae) at Month 12 and Month 24;
- (11) Renal function change from Month 1 (Week 4) to Month 12 and Month 24;
- (12) Evolution of renal function (eGFR by MDRD4) from Month 1 to Month 12 and Month 24 (slope analyses).

The analyses on efficacy endpoints and renal function will be based on the Full Analysis Set. Selected parameters will be analyzed on the Per-Protocol Set as well.

A Z-test based comparison will be performed for the following composite endpoints: tBPAR or eGFR (MDRD4) < 50 mL/min/1.73m² at Month 24, composite endpoint of tBPAR excluding grade IA rejections or eGFR (MDRD4) < 50 mL/min/1.73m² at Months 12 and 24, endpoint of tBPAR, graft loss, death or eGFR < 50 mL/min/1.73m² at Months 12 and 24, and endpoint of tBPAR, graft loss, death, or loss to follow-up at Months 12 and 24.

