### 2.1 Data Analysis General Information

The cut-off day is defined as the latest study day before and up to which data will be used in the analysis on an individual patient level. The cut-off date for 12-month analysis will be the day of Month 12 Visit (specifically, Date of Discontinuation/Study Phase Completion as recorded on the Month 12 Disposition eCRF) + 2 Weeks, but no later than Day 450 (upper limit of Month 12 analysis window). For the 24-month analysis, there will be no cut-off day. All data in the clinical database will be used for the analyses.

Data listings will include all data collected up to the cut-off date for the 12-month analysis, or all data recorded in the database for the 24-month analysis.

For summary tables and figures, the following rules will be applied unless otherwise indicated:

- Categorical data will be summarized by frequencies and percentages. Continuous data will be summarized by mean, median, standard deviation, minimum and maximum and the number of non-missing data points.
- All AE/Infection, notable events, CMV information, EBV information and other events of interest will be summarized based on all collected events with onset on or after the first day of study medication up to the cut-off date or seven days after last dose of study medication. For SAE/infection and death, all events will be summarized.
- All lab or vital sign tables will include data up to the cut-off date or two days after last dose of study medication (on-treatment analysis);

- Efficacy and renal function analyses will be primarily based on all available data including those after study medication discontinuation; as a sensitivity analysis they will include only data up to two days after last dose of study medication (on-treatment analysis). Patients will be censored for the time to event analyses if they do not have an event. For on-treatment analysis, the censoring day is two days after discontinuation of study medication or the last contact day, whichever is earlier; for analysis regardless of on-treatment or off-treatment, the censoring day is the last contact day.
- For post-baseline continuous values, for a given patient, if multiple numeric measurements for a given variable are reported within the same visit window (see the definition for visit windows in [Section 4.1](#)), the following rule will be applied:

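### SAP 2.7.3.1 analyses CKD-EPI and cystatin C eGFR only on treatment, an unexplained exception that leaves the FAS MDRD4 result with no all-data check by another formula

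*SAP*

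**What the plan says.** Protocol 2.2 names as a secondary objective "Renal function by Cystatin C-based and other alternate formulae (e.g. CKD-EPI"). Protocol 9.5.2 turns this into secondary variable (10), "Renal function (eGFR by MDRD4, CKD-EPI and Cystatin C-based formulae) at Month 12 and Month 24", and states: "The analyses on efficacy endpoints and renal function will be based on the Full Analysis Set". Protocol 9.1 has the FAS analysed by randomised assignment under the intention-to-treat principle.

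SAP 2.1 sets the general rule: "Efficacy and renal function analyses will be primarily based on all available data including those after study medication discontinuation". The on-treatment restriction comes second: "as a sensitivity analysis they will include only data up to two days after last dose of study medication (on-treatment analysis"). The list containing these rules opens with "the following rules will be applied unless otherwise indicated".

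For CKD-EPI and cystatin C, SAP 2.7.3.1 then specifies that the "analyses will be based on on-treatment analysis without imputation", and adds: "A two-sided t-test will be performed to compare the two treatment groups at each visit". It names no analysis set and no all-data version. SAP 2.7.3.2 gives MDRD4 the FAS with multiple imputation, and repeats the by-visit outputs on treatment.

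**The concern.** The alternate formulae show whether the renal result depends on the MDRD4 equation. Cystatin C matters most, because it is the only one of the three that does not use creatinine. For these two formulae the analysis that SAP 2.1 ranks as sensitivity becomes the only one.

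At Months 12 and 24, the time points of the endpoint, anyone who stopped the regimen more than two days earlier contributes nothing. Stopping happens after randomisation, in an open-label comparison of different regimens, and may be related to renal function. The t-test then compares those who stayed on each regimen, not the randomised groups. The main MDRD4 result, which does follow the randomised groups, has no second formula analysed in the same way.

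**Working it through.** **Figures in the plan.** The documents give no power, sample size or discontinuation rate for these endpoints, so there is no stated figure to reproduce. The check is a comparison of texts, followed by an illustration of size.

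**Is there a data reason for the exception?**
- CKD-EPI (SAP 4.5.3) uses serum creatinine, age, sex and race, the same inputs as MDRD4 (SAP 4.5.1). A patient with an MDRD4 value also has a CKD-EPI value.
- Cystatin C is in the central laboratory panel. Protocol Table 6-1, note 7, keeps all central tests going to Month 24 for patients off regimen. Note 10 and the text after it set their visits at Months 6, 9, 12, 18 and 24.
- The readable part of the SAP change history gives no reason (one entry is blacked out).

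The samples needed for an all-data analysis are therefore planned.

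**Shift in the arm difference.** Let d be the share of an arm off regimen at the visit and D their eGFR deficit against those still on regimen. The all-patient mean is (on-treatment mean) − d × D, so on-treatment selection raises an arm's mean by d × D. With a common deficit, the EVR minus MPA difference shifts by (dE − dM) × D.

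Assumptions: dM = 20%; dE = 20 to 35%; D = 5 to 15 mL/min/1.73m2. The 20% borrows the Month 12 per-protocol exclusion rate in Protocol 9.7, which is not a discontinuation rate.
- dE = 20%: (0.20 − 0.20) × D = 0 for any D.
- dE = 25%: 0.05 × 5 = 0.25 to 0.05 × 15 = 0.75.
- dE = 30%: 0.10 × 5 = 0.50 to 0.10 × 15 = 1.50.
- dE = 35%: 0.15 × 5 = 0.75 to 0.15 × 15 = 2.25.

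A positive value favours EVR. If more MPA patients stop, the sign reverses.

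**Scale.** SD is taken as 20, from the ASSET results in Protocol 1.1 (SDs 19.5 and 20). The difference detectable with 80% power at two-sided 0.05 is (1.96 + 0.84) × 20 × √(2/n):
- 1020 per arm: 2.48.
- 816 per arm (20% dropped): 2.77.
- 714 per arm (30% dropped): 2.97.

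**Effect on the t-test.** Suppose the true all-patient difference is zero. With 816 in each arm (a simplification), SE = 20 × √(2/816) = 0.99. A shift of 0.5, 1.0 or 1.5 raises the two-sided rejection rate from 5% to about 8%, 17% or 33%. With 714 per arm the rates are about 8%, 16% and 29%.

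**Graft losses.** The zero after graft loss belongs to the eGFR imputation rules (SAP 4.2.1), so it does not apply in 2.7.3.1. Leaving a share g of graft losses out, instead of scoring them zero, raises an arm's mean by g × mean. With the ASSET means of 51.7 to 57.1, g = 1% gives 0.52 to 0.57 and g = 3% gives 1.55 to 1.71. Most of this cancels in the arm difference if graft loss is similar in the two arms.

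**The case against.** **The comparison with MDRD4 can be read.** A reader might infer that the formulae are never compared on the same patients. SAP 2.7.3.2 repeats the MDRD4 summaries, t-test and plot on treatment, so a like-for-like comparison exists there. This stands; only the all-data counterpart is missing.

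**The SAP allows exceptions.** A reader might call 2.7.3.1 a contradiction of SAP 2.1. It is not: the rules in 2.1 apply "the following rules will be applied unless otherwise indicated", and SAP section 2 carries a similar reservation about following the protocol. What remains is an exception without a reason.

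**The protocol conflict is narrow.** The FAS defines patients; on-treatment restricts data. Protocol 9.4.3 sets imputation and the zero for graft loss for the primary variable, and 9.5.2 extends those methods only in its MDRD4 paragraph. Omitting imputation for the other formulae therefore breaches nothing. The on-treatment restriction is what departs from intention-to-treat use of the FAS.

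**Discontinued patients do not disappear altogether.** Values up to two days after stopping are kept, so these patients count at earlier visits. SAP 4.2.3 also plans a last-available-value row for laboratory variables, including renal ones. If that covers these formulae, it brings some patients back but clashes with the no-imputation rule in 2.7.3.1.

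**Renal function is also a safety variable.** Protocol 6.5 places it there, and 9.1 makes safety analyses generally on-treatment. But 9.5.2 lists these formulae among the efficacy variables and gives them the FAS.

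**The stakes are modest.** Protocol 6.5 makes MDRD4 the main method for renal endpoints, and the alternate formulae lie outside the testing hierarchy. Both points are correct and limit the weight of the concern.

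**Conclusion.** The concern holds in a limited form. SAP 2.7.3.1 is an unexplained exception to SAP 2.1 and departs from the intention-to-treat use of the FAS that Protocol 9.5.2 assigns to renal function, although the off-regimen samples are planned. The Month 12 and 24 comparisons for two of the three formulae depend on staying on regimen.

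A reader might infer that the planned analysis favours EVR. The documents do not support that, because they give neither discontinuation rates nor eGFR after stopping. The range of 0 to 2.25 mL/min/1.73m2 toward EVR follows from the assumed inputs; it is zero with equal rates and deficits and can reverse. The primary and key secondary conclusions do not rest on these analyses.

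**What to change.** In SAP 2.7.3.1, make the FAS with all available on- and off-treatment data the main analysis for CKD-EPI and cystatin C eGFR, and keep the on-treatment version as the sensitivity analysis. If the exception is intended, state the reason. Say whether the LOCF rows in SAP 4.2.3 apply to these formulae, and reconcile that with the no-imputation wording.

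Using the MDRD4 graft-loss and multiple-imputation rules as well is desirable for comparability, though the protocol does not require it here. Graft loss is a listed reason for leaving the study (Protocol 5.5.9), so all-data analysis alone may not bring these patients back.

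The cost is SAP wording and some programming, with no new samples. The MDRD4 programs can be adapted, but each formula would need its own imputation model. Cystatin C may have more missing values, because Protocol Table 6-1 gives a local-laboratory fallback for creatinine only.
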